6.1 Specimen collection, processing, and shipment

6.1.1 Semen Collection

Semen samples will be obtained at the screening visit (as needed), visit 1, and visit 3. Semen assessment at the screening visit and visit 1 will occur prior to treatment. Samples will be assessed using a standard semen analysis, including assessment of morphology using strict criteria, the SCSA, COMET, and TUNEL. These analyses will allow us to assess sperm motility and

DNA structure, two components frequently affected by ROS. Couples will not be informed of results until the end of the study, as this information could lead to behavior changes. Men will be asked to abstain from ejaculation 2-5 days prior to collection. Samples will be collected by masturbation at the clinical site. Samples will be allowed to liquefy for 30 minutes at 37° C prior to analyses.

6.1.2 *Semen analysis*

Subsequently the initial physical characteristics (e.g. volume, pH) will be recorded. Count and motility will be measured using 5µl of semen loaded on a sperm counting chamber (Microcell, Conception Technologies, San Diego, CA) (76). Semen smears will be made for each sample, stained by the Papanicolaou method, and shipped to a central laboratory for assessment of sperm morphology by a single technician, using strict criteria defined by WHO 5 (77). Semen analyses will be conducted at the screening visit, study visit 1 (prior to treatment), and study visit 3 (at 3 months of treatment).

6.1.3 *DNA integrity testing*

DNA integrity needs to be assessed in addition to traditional semen parameters as a significant number of men will have high levels of DNA fragmentation despite a normal semen analysis (39-41). There are three common assays of sperm DNA integrity: two of which measure actual DNA strand breaks (neutral COMET and TUNEL) and one of which measures the potential for strand breaks (SCSA) (78, 79). The SCSA assay is proposed as it is the only DNA integrity testing method that is standardized in a commercial laboratory. It is the only test in wide clinical use.

6.1.4 *SCSA*

6.1.6 COMET

One aliquot of raw semen will be sent to a central laboratory for the COMET assay. The comet assay is one of the simplest methods to measure sperm DNA damage by quantifying the single and double strand breaks. The principle of the assay is that the sperm nuclear DNA is separated in an electric field based on charge and size, which is viewed with a fluorescent DNA-specific dye. The resulting images, which resemble comets with an intact head and tail, determine the extent of DNA damage based on the intensity of staining and morphology of the comet. The COMET assay will be conducted on the study visit 1 sample (prior to treatment) and study visit 3 sample.

6.2 Compliance

Compliance and cross-over will be assessed via two mechanisms: 1) pill counts and 2) measurement of Vitamin E (alpha-tocopherol), L-carnitine, and zinc (and, if possible, Vitamin C and selenium) in blood. Compliance and cross-over will be assessed by these 2 mechanisms at study visits 2, 3, and 4 (corresponding to months 1, 3, and 6 of treatment). At study visit 1 (month 0 of treatment), a baseline measurement will be established.

6.2.1 Measurement of vitamin levels

A random sample of 10% of blood samples (as done in the SU.VI.MAX study (83)) obtained at study visits 2, 3, and 4 will be shipped to a laboratory such as the Clinical Pharmacology Analytical Services Laboratory (CPAS) in the Department of Experimental and Clinical Pharmacology in the College of Pharmacy at the University of Minnesota (<http://www.pharmacy.umn.edu/cpas/services/index.htm>). All three vitamins will be measured using a LC-MS/MS method. Internal standards are commercially available. These samples will allow us to assess for compliance. As placebos will also be samples, we will also be able to assess for cross-over.

6.3 Dietary assessment

A previous observational study showed that a health-conscious diet is associated with a decrease in sperm DNA fragmentation, suggesting that natural antioxidants are beneficial to sperm (31). However, another observational study using food frequency questionnaires failed to find an association between any antioxidant measure and DNA fragmentation, perhaps because the cohort was comprised of healthy volunteers (32). Therefore, to assess for possible effect modification by baseline dietary composition and vitamin intake, we will assess these through a 24-hour recall during the 1st study visit and a food frequency questionnaire at baseline. Secondary analysis could be conducted to examine the relationship between baseline dietary composition and vitamin intake and semen parameters and couple fecundability and fertility over the study period. A second 24-hour recall will be obtained at the 3-month study visit to determine if there were differential changes in dietary composition among treatment groups.

To measure food intake, we will use the validated, self-administered, web-based, 24-hour recall questionnaire, ASA24 and Diet History Questionnaire II. The method allows for collection of detailed intake and portion sizes. It does not affect what an individual chooses to eat on a given day, due to its retrospective data collection. It is administered in close proximity to the intake

6.1.6 COMET

One aliquot of raw semen will be sent to a central laboratory for the COMET assay. The comet assay is one of the simplest methods to measure sperm DNA damage by quantifying the single and double strand breaks. The principle of the assay is that the sperm nuclear DNA is separated in an electric field based on charge and size, which is viewed with a fluorescent DNA-specific dye. The resulting images, which resemble comets with an intact head and tail, determine the extent of DNA damage based on the intensity of staining and morphology of the comet. The COMET assay will be conducted on the study visit 1 sample (prior to treatment) and study visit 3 sample.

6.2 Compliance

Compliance and cross-over will be assessed via two mechanisms: 1) pill counts and 2) measurement of Vitamin E (alpha-tocopherol), L-carnitine, and zinc (and, if possible, Vitamin C and selenium) in blood. Compliance and cross-over will be assessed by these 2 mechanisms at study visits 2, 3, and 4 (corresponding to months 1, 3, and 6 of treatment). At study visit 1 (month 0 of treatment), a baseline measurement will be established.

6.2.1 Measurement of vitamin levels

A random sample of 10% of blood samples (as done in the SU.VI.MAX study (83)) obtained at study visits 2, 3, and 4 will be shipped to a laboratory such as the Clinical Pharmacology Analytical Services Laboratory (CPAS) in the Department of Experimental and Clinical Pharmacology in the College of Pharmacy at the University of Minnesota (<http://www.pharmacy.umn.edu/cpas/services/index.htm>). All three vitamins will be measured using a LC-MS/MS method. Internal standards are commercially available. These samples will allow us to assess for compliance. As placebos will also be samples, we will also be able to assess for cross-over.

6.3 Dietary assessment

A previous observational study showed that a health-conscious diet is associated with a decrease in sperm DNA fragmentation, suggesting that natural antioxidants are beneficial to sperm (31). However, another observational study using food frequency questionnaires failed to find an association between any antioxidant measure and DNA fragmentation, perhaps because the cohort was comprised of healthy volunteers (32). Therefore, to assess for possible effect modification by baseline dietary composition and vitamin intake, we will assess these through a 24-hour recall during the 1st study visit and a food frequency questionnaire at baseline. Secondary analysis could be conducted to examine the relationship between baseline dietary composition and vitamin intake and semen parameters and couple fecundability and fertility over the study period. A second 24-hour recall will be obtained at the 3-month study visit to determine if there were differential changes in dietary composition among treatment groups.

To measure food intake, we will use the validated, self-administered, web-based, 24-hour recall questionnaire, ASA24 and Diet History Questionnaire II. The method allows for collection of detailed intake and portion sizes. It does not affect what an individual chooses to eat on a given day, due to its retrospective data collection. It is administered in close proximity to the intake

day minimizing recall issues. The ASA24 format and design is based on a modified version of the interviewer-administered Automated Multiple Pass Method (AMPM) developed by the US Department of Agriculture. The ASA24 consists of a respondent web site (<https://asa24.westat.com/>) and a researcher website (<https://asa24.westat.com/researchersite.html>). The respondent website guides the participant through the completion of a 24-hour recall for the previous day from midnight to midnight using a dynamic user interface. Information and instructions on the ASA24 can be found at https://asa24.westat.com/assets-r/docs/ResearcherSite_Instructions.pdf and a demonstration at <http://asa24demo.westat.com/>. The male participants will complete the ASA24 on the day of study visit 1 and study visit 3.

The Diet History Questionnaire II (DHQ II) is a food frequency questionnaire (FFQ) developed at the Risk Factor Monitoring Branch. The DHQ II consists of a respondent website and a researcher website. The respondent website guides the participant through the completion of a questionnaire regarding portion size, usual intake, and dietary supplements over the past year. Information and instructions on the DHQ II can be found at <http://appliedresearch.cancer.gov/dhq2/> and a demonstration at <https://appliedresearch.cancer.gov/cgi-bin/dhq2.pl?module=2&method=1>. In summary, the DHQ has been validated as a measure of frequency and nutrient assessment. The full and extensive list of the 176 nutrients, dietary constituents, and food groups assessed with the DHQ is available on the website. Both male and female participants will complete the DHQ II at screening.

6.4 Male urinary testing for environmental contaminants

Urine samples will be obtained from male participants at the visit 1 for future assessment for common environmental contaminants such as Bisphenol-A (BPA). Samples will be collected into BPA-free collection containers at the clinical site and transferred to BPA-free cryovials by study staff. Samples will be stored frozen until shipped in batches to a central laboratory for analysis.

6.5 Stress biomarker testing

A first morning (basal) salivary sample will be obtained from male and female participants using a salivary collection device. Participants will be told to collect the sample immediately upon awakening before eating, drinking, smoking or brushing their teeth. Samples from males will be collected around the time of study visit one and returned at the time of study visit one or by prepaid overnight shipping. Females will collect their sample shortly after their screening visit and return the sample via prepaid overnight shipping. Samples will be stored at -20°C until analysis. Samples will be analyzed for stress biomarkers such as amylase and cortisol. Participation in this part of the study will be optional.

6.6 Male laboratory testing (central core laboratory)

The core lab will analyze the blood samples from the males at study visit 1 (prior to treatment) for total testosterone, LH, FSH and Vitamin D25-OH. They will also analyze the blood samples from the males at study visit 3 for Vitamin D25-OH.

6.7 Male sunscreen usage

There is increasing concern that benzophenone (BP)-type ultraviolet filters, used in sunscreens, are absorbed by the skin and act as endocrine disruptors (84). Sunscreen ingredients have been demonstrated *in vivo*² and *in vitro*³ to act as endocrine disruptors: either affecting estrogen (those containing PB-2 [tetrahydroxybenzophenone] and BP-8 [3,4-dihydroxy-4-methoxybenzophenone]) (85,87) while other UV filters (13 of 29 filters), disrupted progesterone's effect on sperm calcium ion channels (86). While not all UV filters have been associated with a reduction in male fertility, the SEBI (Sun Exposure and Behaviour Inventory) (88) questionnaire will be used to evaluate whether or not men using more sunscreen will experience less fecundity. Future analysis of repository blood or urine samples may be used to more accurately specify which UV filters are responsible for less fecundity.

Sunscreens with PABA block the specific sunlight spectrum responsible for cutaneous synthesis of vitamin D (89). Since the MOXI preparation contains vitamin D, the frequency and amount of both sun exposure and sunscreen usage should be documented.

6.8 Quality of Life (QOL) Measures

Mood, quality of life, and sexual function will be assessed at baseline in both males and females. Quality of life will be assessed by the Medical Outcomes Survey (PHQ-9) and Short Form 12 (SF-12). Female sexual function will be assessed by the Female Sexual Function Inventory (FSFI) along with the Female Sexual Distress Scale (FSDS). This measure is considered the "gold standard" paper and pencil assessment of sexual function and has excellent psychometric properties. Male sexual response will be assessed by the International Index of Erectile Function (IIEF), a multidimensional scale for assessment of erectile dysfunction. The measure addresses the relevant domains of male sexual function (erectile function, orgasmic function, sexual desire, intercourse satisfaction, and overall satisfaction). We will assess hypogonadal symptoms with the Androgen Deficiency and the Aging Male quantitative (qADAM) questionnaire and psychosexual function with the Psychosexual Daily Questionnaire (PDQ). We will assess quality of life relating to infertility and treatment with the FertiQoL survey. There may also be some impact on fertility and we will investigate this in our study. We will use two simple scales to evaluate sleep, the STOP BANG questionnaire for sleep apnea, and the Epworth Sleepiness Scale. (See Appendices)

6.9 Early Pregnancy Ultrasound

A transvaginal ultrasound (standard for first trimester imaging), will be scheduled, ideally between 6 2/7 and 7 2/7 weeks of gestation; no later than 9 6/7 weeks. This ultrasound confirms estimated date of delivery, and in the case of loss, documents likely developmental stage at the time of the loss (e.g. empty gestational sac, fetal pole not heart rate, normal fetal pole). Presence and size of gestational sac, presence and size of yolk sac, presence of fetal pole and crown-rump length, and presence of cardiac motion and heart rate will be recorded. With minimal costs, ultrasounds achieve 2 study goals. They serve as an incentive to subjects for participation and compliance with study protocols and they provide estimates of miscarriage and clinical pregnancy rates.

6.10 Ascertainment of Pregnancy Outcomes

Participants will be encouraged to report outcome (miscarriage, ectopic, abortion, live birth) and answer follow-up questions specific to that outcome (for miscarriage: date miscarriage identified and for live birth: date of delivery, gestational number, birth weight, gender, and obstetrical complications).

6.11 Pregnancy Registry

All subjects who deliver will be encouraged to participate in our Pregnancy Registry which currently provides infant follow up till age 3. This is currently a separate protocol and we will also obtain separate informed consent for participation in this protocol.

6.12 Biologic Repository

We will use the RMN biorepository as a biological specimen's bank at baseline prior to randomization in both females and males. This Biorepository will serve a two-fold purpose. First, it can serve as a repository to run additional serum assays for novel markers of infertility or treatment success that are discovered while the study is ongoing. Second, it will serve as a source of samples for further studies including proteomics, metabolomics, etc. We will collect whole blood, serum, and urine from female and male participants, if consented. We will also collect semen from male partners, if consented. Subjects will be able to opt in or opt out of these studies via separate signature on the consent form. We will also store leftover serum samples for additional post hoc studies. Study subjects will be separately consented to store and use their leftover serum samples from the study and will similarly be able to opt out. Further details of specimen processing can be found in the Manual of Operations and Procedures.

6.13 Central Core Laboratory

Screening labs to determine eligibility will be run in the local RMN site labs. Given the variability of assays between labs, assays will be performed in a central lab at the Ligand Assay Core lab at the University of Virginia.

7 Data Analysis

7.1 Internal Pilot

We will be conducting an internal pilot study with a three-fold objective. The objective of the internal pilot is 1) to determine the distribution of various types of semen abnormalities in the study population, 2) to examine the effect of our antioxidant formulation on male semen parameters and DNA integrity at 3 months of treatment compared to controls, and 3) to determine the feasibility of the proposed recruitment paradigm.

The first 120 men enrolled in the MOXI trial will be included in the internal pilot. The 120 men will complete the entire MOXI protocol. Once the first 120 men enrolled in MOXI have completed study visit 3, the DCC will complete the data analysis for the internal pilot. After data cleaning and transformations, if needed, semen parameter measures will be analyzed using a generalized linear mixed model (including random effects for site if necessary) or generalized linear model (if fixed effects for site are used). Interaction terms will be used to determine the extent to which the change in semen parameter measures differs by type of baseline semen abnormality (oligospermia, asthenospermia, high DNA fragmentation), if there is evidence of effect modification, change estimates will be determined for type.

If we assume that 50% of the males will have low motility (<40%) after taking into account potential dropouts and that the drop-outs will be randomly distributed, we should have 30 men in each group. Based on Fedder et al. we can assume that the percentage of sperm motility at the end of treatment in antioxidant group can be increased by 32% (SD20%) from basement and that in the placebo group it will be increased by 20 % (SD12%)(83). Furthermore, Khadem et al. (38) reported that DNA fragmentation decreased from 22.1±7.7% to 9.1±7.2% in antioxidant group (38). Under these assumptions, or pilot phase will have 80% power to detect the differences suggested in the literature with $\alpha=0.05$.

Feasibility will be assessed by recruitment pace. We anticipate that the pilot enrollment will be completed by 6 months starting from when all the sites have been initiated to start the trial. Thus 120 couples will be recruited over the 6 months. The pilot goal assumes that recruitment pace will increase over the course of the entire study period.

Assuming we fail to reject the null hypothesis that motility and DNA fragmentation percentage do not differ between the two treatment groups (antioxidant and placebo), the MOXI trial will stop enrolling subjects. Enrolled couples will complete the study protocol. Data analyses will be conducted for the primary and secondary outcomes for the primary study. These results could be used to power a future study should point estimates suggest that male partner treatment with antioxidants increases live birth or pregnancy rates.

Assuming 1) we reject the null hypothesis that motility and DNA fragmentation percentage do not differ between the two treatment groups (antioxidant and placebo) and 2) we determine that the study is feasible, the MOXI trial will continue until a total of 790 couples have been enrolled. Since the primary outcome will not be analyzed for the pilot, it is not thought that adjustments in significance levels will be required for these analyses.

7.2 Primary and Secondary Outcomes

The primary outcome is a live birth resulting from a pregnancy occurring within the 6 months of treatment. Live birth is defined as a delivery of a live infant after 20-weeks gestation. Secondary outcomes include pregnancy, defined by a positive home pregnancy test within the 6 months of treatment. We will conduct an intent-to-treat analysis. Cumulative incidence of live birth and pregnancy will be compared between those couples randomized to antioxidants and those couples randomized to placebo. In addition, discrete-time hazard models will be used to compare time-to-pregnancy between groups. Subsequent subgroup analyses will be conducted to assess for effect modification by type of baseline sperm abnormality. All analyses will include fixed or random effect terms as needed to account for potential site effects.

7.3 Sample Size and Statistical Power

For the power analysis, we assume live birth rates of 35% in the antioxidant group and 25% in the control group, and 17% drop-out (based on drop-out rate in prior RMN trials). A 25% live birth rate was estimated, assuming 5% live birth rate in the first 3 months of timed intercourse and a 20% live birth rate in the 3 clomid/IUI cycles. The 20% live birth rate is the live birth rate in AMIGOS participants receiving up to 3 cycles of clomid/IUI and female partner under the age of 35. Under these assumptions, a sample size of 395 per group will yield 80% power using a two-sided chi square test at $\alpha=0.05$ (Table 2).

Table 2: Sample size estimates under a variety of assumptions

Proportion (%) of live birth in placebo group	Proportion (%) of live birth in antioxidant group	Power (%)	Number of patients per arm with 0% dropout	Total number of patients with 0% dropout	Total number of patients with 17% dropout
20	30	80	294	588	708
20	30	90	392	784	944
25	35	80	328	656	790
25	35	90	440	880	1060
30	40	80	356	712	858
30	40	90	477	954	1150
20	35	80	138	276	332
20	35	90	185	370	446
25	40	80	152	304	366
25	40	90	203	406	490

For subgroup analyses, power is dependent on the distribution of the sperm abnormalities, the control live birth rate and the treatment effect difference (see Table 3).

Table 3: Power for subgroup analyses

Proportion affected (%)	Total N for subgroup	Control Group Pregnancy Proportion (%)	Treatment Effect Difference (%)	Alpha	Power (%)
70	552	20	10	0.05	78
60	474	20	10	0.05	71
50	394	20	10	0.05	63
40	316	20	10	0.05	54
30	236	20	10	0.05	43
70	553	20	15	0.05	98
60	474	20	15	0.05	96
50	395	20	15	0.05	92
40	316	20	15	0.05	85
30	237	20	15	0.05	74
70	553	25	15	0.05	97

60	474	25	15	0.05	94
50	395	25	15	0.05	89
40	316	25	15	0.05	82
30	237	25	15	0.05	69

8 Technical Aspects

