2.8 Statistical Analysis

The primary outcome is a live birth resulting from a pregnancy that is conceived within the 6 months from initiation of treatment. Live birth is defined as a delivery of a live infant after 20-weeks gestation. Secondary outcomes include pregnancy, defined by a positive home pregnancy test within the 6 months of treatment. We will conduct an intent-to-treat analysis. Cumulative incidence of live birth and pregnancy will be compared between those couples randomized to antioxidants and those couples randomized to placebo. In addition, discrete-time hazard models will be used to compare time-to-pregnancy between the two treatment groups. Subsequent subgroup analyses will be conducted to assess for effect modification by type of baseline sperm abnormality (asthenospermia, high DNA fragmentation, oligospermia).

After transformations, if needed, semen parameter measures will be analyzed using a generalized linear mixed model (including random effects for site if necessary) or generalized linear model (if fixed effects for site are used). Interaction terms will be used to determine the

extent to which the change in semen parameter measures differs by type of baseline sperm abnormality (asthenospermia, high DNA fragmentation, oligospermia). If there is evidence of effect modification, change estimates will be determined for each type of baseline sperm abnormality.

For the power analysis, we assume live birth rates of 35% in the antioxidant group and 25% in the control group, and 17% drop-out. Under these assumptions, the power by using a two-sided chi square test at $\alpha=0.05$ would be 0.80.

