3.2 Significance

Although clinical trials suggest that antioxidants have a positive effect on sperm motility, DNA integrity, and pregnancy rates in couples undergoing assisted reproductive technologies, there are significant gaps in our knowledge of their impact on fertility (44). Gaps exist due to limitations in existing literature. 1) A variety of antioxidants at varying doses and duration have been used, precluding a strong conclusion as to whether a specific regimen is beneficial. 2) Most studies have had small sample sizes, usually less than 50 subjects. 3) Studies have utilized heterogeneous populations, limiting ability to combine results of multiple studies. 4) Most studies have used changes in semen parameters or DNA integrity as the endpoint, rather than clinical outcomes. 5) Studies have used antioxidants in conjunction with *in vitro* fertilization with intracytoplasmic sperm injection (ICSI) when measuring effectiveness. This has precluded the possibility of studying antioxidant effects on *in vivo* fertilization, which relies on normal sperm function. Our proposed study will improve generalizability, but still allow for sufficient power to determine benefit among subgroups, and will look at reproductive endpoints including pregnancy, miscarriage, and live birth.

Findings from this research will be significant in that they will likely lead to an effective, natural treatment modality for men with abnormal sperm. An effective, inexpensive, non-invasive treatment for male subfertility would be of significant benefit, as no such treatment has been clinically validated. An effective treatment for men would also reduce the treatment burden on the female partner, lower costs, and provide effective alternatives to couples with religious or ethical contraindications to ART. Even if antioxidants are found not to be of benefit to any

subgroup, this research will help us better understand the reproductive impact of sperm DNA integrity, leading to treatments that could improve fertility, pregnancy outcomes, and offspring health.

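### Table 3's subgroup powers leave out the 17% dropout that Table 2 applies, so they are about 3 to 8 points too high, and no power is given for effect modification

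*Combined protocol and SAP*

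**What the plan says.** Section 7.3 sizes the trial on live birth rates of 25% and 35% and on "17% drop-out (based on drop-out rate in prior RMN trials"). Table 2 carries this through: for 25% versus 35% at 80% power it gives 656 couples with no dropout and 790 in the column headed "Total number of patients with 17% dropout".

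Table 3 then gives 15 subgroup powers, introduced by "For subgroup analyses, power is dependent on the distribution of the sperm abnormalities, the control live birth rate and the treatment effect difference". Its subgroup sizes are 552–553, 474, 394–395, 316 and 236–237. Neither the table nor its introduction mentions dropout. The control column is headed "Control Group Pregnancy Proportion", although the introductory sentence refers to live birth.

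Section 3.2 says the design will "still allow for sufficient power to determine benefit among subgroups".

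On purpose, section 2.8 states: "Subsequent subgroup analyses will be conducted to assess for effect modification by type of baseline sperm abnormality". Sections 4.3 and 7.2 say the same. Interaction terms are specified only for semen measures, in 2.8 and in 7.1: "Interaction terms will be used to determine the extent to which the change in semen parameter measures differs by type of baseline semen abnormality".

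**The concern.** Two tables in one section use different bases. Table 2 says some of the 790 enrolled couples will be lost and rests the main power on 656. Table 3 takes its subgroups as fractions of 790 and loses no one. A reader who compares them finds smaller subgroups credited with more power than Table 2 allows.

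At stake is how the subgroup results will be read. Section 3.2 presents subgroup power as a strength of the design. If the real figures are lower, a null subgroup result may be taken as evidence of no benefit when the comparison had little chance of showing one.

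There is also a gap. Power to detect a treatment effect inside one subgroup is not power to show that the effect differs between subgroups, and the plan names the second as the purpose. For live birth it gives no interaction test, no scale and no power.

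**Working it through.** **Inputs.** From 7.3: two-sided chi-square test, alpha 0.05, 17% dropout, and the rates and sizes in Tables 2 and 3. From 5.5: 1:1 allocation and 790 randomised.

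**Formula.** With n per arm, rates p1 and p2, and p̄ = (p1 + p2)/2:

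power = Φ{ [ |p2 − p1|·√n − 1.96·√(2p̄(1 − p̄)) ] / √( p1(1 − p1) + p2(1 − p2) ) }

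**1. Where Table 3's sizes come from.** 790 × 0.70, 0.60, 0.50, 0.40, 0.30 = 553, 474, 395, 316, 237. These match the printed sizes to within one. Table 2's own step is 656/0.83 = 790.4.

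**2. Reproducing the printed powers with no dropout.** Take the 40% row at 20% versus 35%, with n = 316/2 = 158:
- numerator: 0.15 × √158 − 1.96 × √0.39875 = 1.886 − 1.238 = 0.648
- denominator: √0.3875 = 0.6225
- power: Φ(1.041) = 85.1% (printed 85)

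All 15 rows reproduce this way within 0.6 points.

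**3. Comparison with Table 2's 17% dropout column.**

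| Rates | Table 2: enrolled needed | Table 3: power credited |
|---|---|---|
| 20% vs 35% | 332 for 80%; 446 for 90% | 316 gives 85%; 395 gives 92% |
| 25% vs 40% | 366 for 80%; 490 for 90% | 316 gives 82%; 474 gives 94% |

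**4. Applying the dropout.** 656 × 0.70, 0.60, 0.50, 0.40, 0.30 = 459, 394, 328, 262, 197. The same 40% row now has n = 262.4/2 = 131.2. The numerator is 1.718 − 1.238 = 0.480, so power is Φ(0.772) = 78.0%. The full set:

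| Rates | Basis | 70% | 60% | 50% | 40% | 30% |
|---|---|---|---|---|---|---|
| 20 vs 30 | printed | 78 | 71 | 63 | 54 | 43 |
| | on 656 | 69.8 | 63.0 | 55.3 | 46.4 | 36.6 |
| 20 vs 35 | printed | 98 | 96 | 92 | 85 | 74 |
| | on 656 | 95.2 | 91.8 | 86.4 | 78.0 | 65.6 |
| 25 vs 40 | printed | 97 | 94 | 89 | 82 | 69 |
| | on 656 | 93.2 | 89.1 | 83.0 | 74.0 | 61.4 |
| 25 vs 35 | not in Table 3 | – | – | – | – | – |
| | on 656 | 64.8 | 58.2 | 50.6 | 42.3 | 33.3 |

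The excess runs from 2.8 points (98 − 95.2) to 8.4 points (74 − 65.6).

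**5. Subgroup share needed for 80% power.** Solving the formula gives total N of 276 (20 vs 35), 304 (25 vs 40), 586 (20 vs 30) and 657 (25 vs 35). Dividing by 790 and then by 656, the required share rises:
- 20 vs 35: from 35% to 42%
- 25 vs 40: from 38% to 46%
- 20 vs 30: from 74% to 89%
- 25 vs 35: on 656, no proper subgroup reaches 80%

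**6. Effect modification, for scale only.** The documents give no inputs, so these are assumptions: a Wald test on the difference of two risk differences, equal control rates, 656 couples, and subgroup shares of 30 to 70%. At a 20% control rate, power is 29–34% for an effect of 10 points against 0 in the remaining couples, 54–63% for 15 against 0, and 27–32% for 15 against 5.

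**The case against.** The strongest reply is that each printed power is right for the N beside it, and that Table 3 agrees with Table 2's zero-dropout column (276 for 80% at 20% versus 35%; 304 at 25% versus 40%). That is so. The fault is the basis, not the calculation. But the section assumes 17% dropout, and nothing tells the reader that Table 3 sets it aside.

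A second reply is that 2.8 and 7.2 specify intent-to-treat, so all 790 stay in the analysis. This does not restore the printed figures. If dropouts are counted as having no live birth (an assumption: both rates multiplied by 0.83, N kept at 790), power falls further: 67/61/53/44/35 for 20 versus 30, 94 down to 63 for 20 versus 35, and 91 down to 58 for 25 versus 40. The two 40% rows for a 15-point effect become 75 and 71. What stands is that the table must name its convention. The 656 basis is the one Table 2 uses.

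Third, subgroup analyses are tertiary aims (4.3), the plan never promises interaction power or sets an 80% threshold for subgroups, and the printed table already shows every 10-point row below 80%. This stands as a limit on weight. The absence of interaction power is missing detail on a tertiary aim, not an error in the table. Section 3.2 does not cite Table 3, so the link between them is an inference, though Table 3 is the only subgroup power in the documents.

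**Conclusion.** The point holds. Table 3 overstates within-subgroup power by about 3 to 8 points and conflicts with Table 2's 17% dropout column. Both 40% rows for a 15-point effect fall below 80%, and rows at 80% or more go from 8 of 15 to 6. At the trial's own planning rates, no listed subgroup exceeds 65%. These figures rest on the section's 17% dropout, on dropouts being spread evenly over arms and subgroups, and on Table 2's convention that they leave the analysis; counting them as non-events makes the shortfall larger. The documents contain no power for effect modification, and any figure for it depends on assumptions from outside them. The consequence is confined to subgroup claims: the sample size, primary test and pilot rule do not rest on Table 3.

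**What to change.** - Recompute Table 3 on 656 couples (subgroup sizes about 459, 394, 328, 262 and 197) with the powers in the working, and add the 25% versus 35% case (65/58/51/42/33).
- Add a note that the table allows for 17% dropout, how dropouts are treated, and that it covers treatment tests within one subgroup only. If the analysis will count dropouts as non-events, use the diluted-rate figures and say so.
- Change the control column header to live birth, in line with the introductory sentence, once the authors confirm that this was meant.
- In 3.2, replace the sufficiency claim with a statement that subgroup and effect-modification analyses are exploratory.
- Interaction power is optional. If quoted, give it as a range with its assumptions, not as one number.

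The cost is a table and wording revision. Nothing in the design changes; the stated subgroup powers become less favourable.
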